### 5.3.7 Dose Modifications

RXC004 dose reduction and interruption are permitted. Nivolumab dose reduction is not permitted but dose interruption/delay is permitted.

RXC004 may be dose interrupted (withheld) for up to 14 days until a clinically significant (any grade) and/or a grade  $\geq 3$  related adverse event resolves to baseline or  $\leq$  grade 1. Patients that experience a RXC004 related adverse events that do not resolve to baseline or  $\leq$  grade 1 after 14 days of dose interruption/delay despite appropriate treatment must be discussed with Sponsor, before re-starting RXC004.

Adverse events that are assessed as being causally related nivolumab should be managed as per the Nivolumab Toxicity Management and Dose Modification Guidelines (Appendix 8). If either agent alone is interrupted or discontinued for a related-AE the other agent (nivolumab or RXC004) may be continued if the patient is judged (by the investigator) to be receiving clinical benefit. If a patient continues in the study on nivolumab alone, this treatment may be continued for a maximum of 12 months in total.

### 5.3.8 Study Treatment discontinuation Criteria

RXC004 and nivolumab dose interruption and stopping criteria are detailed for in Table 6

**Table 6 Module 2 Dose Interruption and Stopping Criteria**

Event	Action

Colitis events            (e.g. Colitis, ileitis, enterocolitis etc)
	

Grade 1
	
If receiving RXC004, either as monotherapy or in combination with nivolumab;            Reduce RXC004 to a lower dose and manage as per Appendix 5 (and Appendix 8 if applicable)

Grade 2
	
If receiving RXC004, either as monotherapy or in combination with nivolumab            Interrupt RXC004. Manage as per Appendix 5 and Appendix 8 if applicable. When event has resolved to Grade <math>\leq 1^a</math> and steroids tapered to <math>\leq 10</math> mg of prednisone per day (or equivalent), resume RXC004 at a lower dose and nivolumab (if applicable) at 480 mg once every month.            If event re-occurs after re-starting study treatment, then RXC004 and nivolumab (if applicable) should be permanently discontinued.

Grade 3
	
If receiving RXC004 monotherapy;            Interrupt RXC004. Manage as per Appendix 5 When event has resolved to Grade <math>\leq 1^a</math> and steroids tapered to <math>\leq 10</math> mg of prednisone per day (or equivalent), resume RXC004 at a lower dose.            If event re-occurs after re-starting study treatment, then RXC004 should be permanently discontinued.              If receiving RXC004 in combination with nivolumab; permanently discontinue both agents and manage as per Appendix 5 and Appendix 8.

Event	Action
Grade 4	If receiving RXC004, either as monotherapy or in combination with nivolumab; Permanently discontinue study treatment (both agents if applicable). Manage as per Appendix 5 and Appendix 8
Dysgeusia events	
Grade 1 or 2	RXC004 related; Consider dose reduction, depending on clinical symptoms Manage as per Appendix 6 Interrupt RXC004 treatment if dysgeusia is associated with >5kg weight loss from baseline
Grade 2 associated with a 10-20% decrease in body weight	RXC004 related; Manage as per Appendix 6 Reduce RXC004 to a lower dose.
Grade 2 associated with a >20% decrease in body weight	RXC004 related; Manage as per Appendix 6 Permanently discontinue RXC004. Nivolumab can continue if clinical benefit is judged by investigator for a maximum of 12 months total treatment.
Other adverse events	
Any event that meets discontinuation criteria for nivolumab (see Appendix 8)	Permanently discontinue nivolumab. RXC004 can continue, if clinical benefit is judged by investigator.

Event	Action
Any event that meets nivolumab treatment hold (see Appendix 8)	Interrupt nivolumab and manage as per Appendix 8. Nivolumab can be re-started when event is resolved to $\leq$ Grade 1 and any steroid taper completed (to 10mg prednisone equivalent). RXC004 can continue whilst nivolumab is held, if the patient is judged (by the investigator) to be receiving clinical benefit.
Grade 3-4 toxicity (1 st event)	RXC004 related;  Interrupt RXC004 and provide supportive care, resume at the next lowest dose level when resolved (grade $\leq$ 2 or returns to baseline). Interruptions >14 days should be discussed with Sponsor before re-starting.  Nivolumab related;  See guidelines in Appendix 8
Grade 3-4 toxicity (subsequent recurrence of a previously experienced event)	RXC004 and/or nivolumab related; Permanently discontinue study treatment
All Grade events	Study treatment can be discontinued for any clinically significant AEs that in the investigator's opinion warrants treatment discontinuation.

Event	Action
Bone events	
Confirmed RXC004 related fragility bone fracture (excluding grade 1 vertebral deformities)	Permanently discontinue RXC004. Nivolumab can continue, if clinical benefit is judged by investigator for a maximum of 12 months total treatment.
Patients with a DXA scan showing $\geq 7\%$ worsening in BMD at lumbar spine or total hip compared to baseline	Permanently discontinue RXC004. Nivolumab can continue, if clinical benefit is judged by investigator for a maximum of 12 months total treatment.
An individual increase in $\beta$ -CTX of $\geq 350$ pg/ml from the baseline (screening) value or in individual measurement of $\geq 1000$ pg/ml	Permanently discontinue study treatment unless the patient has received clinical benefit (investigator assessment) and continued treatment is warranted.
COVID-19 infection	
Positive COVID-19 test	Interrupt RXC004, until acute symptoms have resolved. Interruptions $>14$ days should be discussed with Sponsor before re-starting.
Surgery	Interrupt RXC004 (max. 14 days b ), resume at full dose. RXC004 should be stopped 3 days prior to surgery and resumed approx. 10 days later. If the wound has not healed a further 7 days are permitted prior to re-starting RXC004 at the discretion of the Investigator and with approval of Sponsor Physician.  No stoppage is required for biopsy procedures.
Vomiting	If vomiting occurs shortly after RXC004 is swallowed, the dose may be replaced if all of the intact capsules can be counted. Resume with the following scheduled dose.
Missed RXC004 dose	Allowed to take the scheduled dose up to 4 hours after the scheduled dose time. If greater than 4 hours, the missed dose should not be taken and patient should continue with next dose at allotted time.

a. Attempts should be made to confirm that the colitis has resolved to Grade  $\leq 1$  (e.g. normalised CRP or fecal calprotectin if raised during event; GI appearance normalised on X-ray/CT or endoscopy) before restarting RXC004.

b. RXC004 interruptions of greater than 14 days may be allowed for patients judged by investigator to be clinically benefiting from study treatment, and only after consultation with Sponsor

### 5.3.9 Biomarker Samples

An archival or a newly acquired tumour biopsy will be requested from every patient enrolled in the study. Archived/newly acquired biopsies are optional (but encouraged) in the Module 2 dose escalation.

In all patients participating in the study, the taking of non-mandatory tumour biopsies will be encouraged and can be taken from each patient at up to 3 time points during the study;

1. At baseline (prior to first dose of study treatment)
2. During study treatment dosing (see SoA for biopsy timings)

At the time of tumour biopsy, blood samples for assessment of PK and blood borne biomarkers will be taken; Analysis of these samples will include, but not be restricted to, functional Wnt pathway inhibition, immune gene signature and immune cell infiltration.

### 5.3.10 Exploratory Assessments

The circulating soluble factors and PBMC pharmacodynamic samples (all sites) will be obtained at C0D1 (prior to first dose) and on C1D15 and Day 1 of each cycle thereafter. These samples may be used to examine gene and protein expression changes, including measurement of inflammatory markers. Fresh whole blood (from selected sites of close proximity) will be obtained at C0D1 (prior to first dose), and pre-dose at C1D15 and C2D1. Fresh whole blood may be stained for cell surface markers to identify immune cell populations present in the circulation before and after treatment. Circulating tumour DNA (ctDNA) and RNA (ctRNA) will be collected pre-dose at C0D1, post-dose on C1D15 and Day 1 of each subsequent cycle and at treatment discontinuation. Analysis of total amounts and/or tumour mutations (including Wnt pathway aberrations) in ctDNA samples may be evaluated and correlated to patient response.

## 5.4 Module 3

Module 3 will investigate the PK, Wnt pathway inhibition, incidence/severity of Wnt pathway related adverse events and anti-tumour activity of RXC004 when given at 2 different intermittent dosing schedules, in a selected group of patients with Wnt ligand dependent advanced solid tumours.

Following the completion of Module 1, the 2mg QD dose was selected as the recommended starting dose for Phase 2 studies, with options of interruptions and dose reductions to manage potential toxicities. The most frequently occurring treatment related AEs in module 1 (all doses) were fatigue (52%), nausea (44%), decreased appetite (40%), dysgeusia (40) and

vomiting (24%). The median RXC004 exposure in Module 1 was approximately 7 weeks so these adverse events were generally observed during the first two treatment cycles. Of the observed adverse events, only dysgeusia, a known on-target toxicity of Wnt pathway inhibitors, was observed to be dose-related and 4 out of 6 patients in the 2mg cohort reported dysgeusia within the first 2 treatment cycles. Module 3 will explore whether intermittent dosing schedules have the potential to deliver clinical anti-tumour activity in selected patients with Wnt ligand dependent tumours and whether intermittent dosing, giving short treatment breaks, has the potential to reduce incidence of treatment related toxicities such as dysgeusia. If so, an intermittent dosing schedule could be a future alternative to dose reduction in the management of treatment related adverse events.

#### **5.4.1 Module 3: Study Objectives**

The study objectives are detailed in Section 1.9

#### **5.4.2 Module 3 Eligibility Criteria**

##### **5.4.2.1 Module 3 Specific Inclusion Criteria**

Module 3 specific inclusion criteria can be found in Section 2.1.3. Patients must fulfill all of the core and Module 3 specific inclusion criteria in order to be eligible to receive study treatment in Module 3. The core inclusion criteria are detailed in Section 2.1.1

##### **5.4.2.2 Module 3 Specific Exclusion Criteria**

There are no Module 3 specific exclusion criteria. Patients must not meet any of the core exclusion criteria in order to be eligible to receive study treatment in Module 3. The core exclusion criteria are detailed in Section 2.

##### **5.4.2.3 Restrictions**

Study restrictions are explained in Section 2.3 and prohibited concomitant treatments are explained in Section 2.3.1.

##### **5.4.2.4 Pre-screening for tumours with RNF43 mutations and RSPO fusions**

All patients enrolled into Module 3 must have Wnt dependent solid tumours, defined as;

- Any solid tumour with a predicted loss of function RNF43 mutation (see Appendix 10 for details).
- Any solid tumour with a RSPO fusion (see Appendix 10 for details)
- Biliary tract cancer

- Thymus cancers (thymic and thymoma WHO Classification)

Eligible patients with RNF43 mutations or RSPO fusions, detected either in a tumour sample or in circulating tumour DNA (CTDNA), will be identified by either a central genetics screening approach or local laboratory assessments. Patients with colorectal, pancreatic, gastric, prostate or squamous non-small cell lung cancers may submit archival tumour samples to the central genetic screening (study pre-screening).

Diagnostic/archival tumour FFPE samples may be sent to Northern Genetics Service for central genetic screening for RNF43 mutations and RSPO fusions. This is an ISO 15189 accredited NHS laboratory and part of the Newcastle NHS Trust, UK. During analytical validation, the RNF43 iPLEX assay, that detects 33 known RNF43 loss-of-function variants, performed at 100% for Analytical Sensitivity / Positive agreement (PPA) and 100% for Analytical Specificity/ Negative agreement (NPA). During analytical validation, the RSPO iPLEX assay, that detects 7 known RSPO gene fusions, performed at 100% for Analytical Sensitivity / PPA and 100% for Analytical Specificity / NPA. See Appendix 10 for a list of the mutations and fusions covered by these iPLEX tests. In addition, patient diagnostic/archival tumour biopsy samples will also be tested in a mini-panel DNaseq for the following genes: RNF43, APC, CTNNB1, AXIN1, AXIN2, BRAF, MLH1 and KRAS. During analytical validation the custom 8 gene DNaseq panel, analyzed on an Illumina MiSeq platform and processed through a SOPHiA DDM pipeline (CCCP\_A\_QIA\_v1), performed with an Analytical Sensitivity / PPA of 99.03%, and an Analytical Specificity / NPA of 100%. RNF43 predicted loss-of-function mutations detected in this DNaseq assay will also be eligible, and could include mutations or aberrations in RNF43 beyond those listed in Appendix 10. As RNF43 is a tumour suppressor gene in context of the Wnt pathway, further screening is likely to identify previously unseen RNF43 loss-of-function mutations. The remaining 7 genes on the DNaseq panel will be used to retrospectively investigate whether aberrations in these genes correlate with response to therapy (exploratory analysis).

Data from central genetic screening will be shared with investigators to aid future treatment decisions.

Patients with any solid tumours with predicted loss of function RNF43 mutations or RSPO fusions from other local testing of blood or tumour will also be eligible to enter the study, provided that the assay used for testing has adequate analytical validation for this purpose (i.e. fully CE-marked for the purpose of investigating RNF43 mutations or RSPO fusions; partially CE-marked for their analytical performance or having achieved a minimum

validation specification of >90% for Analytical Sensitivity / PPA and >95% for Analytical Specificity / NPA for the detection of the aberrations in the genes of interest and performed in an ISO accredited, CLIA or CAP accredited lab). If aberrations are detected by local tests that are not included in the list in Appendix 10, these may be included in the study on discussion with the Sponsor.

### 5.4.3 Dose Rationale

In Module 3, intermittent schedules of RXC004 will be investigated. The intermittent schedules will use 2mg QD RXC004, which has already shown to be safe and tolerated when used continuously in Module 1 of this study. This dose delivers Cmin values > 3-fold IC50 in patients, which is expected to lead to >50% Wnt pathway inhibition, while also being safe and tolerable.

Module 1 opened in 2018 with a RXC004 dose of 10mg once daily, but the dose was not tolerated in the first patient and the Module 1 dose escalation was restarted on 18th March, 2019 with 0.5mg RXC004. As of the 30th July, 25 patients have been dosed with RXC004 monotherapy in Module 1 of the study at doses of 0.5mg (4), 1mg (3), 1.5mg (7), 2mg (6), 3mg (4) and 10mg (1)

At doses up to and including 2 mg QD, the most common treatment related AEs were fatigue (10/20 patients), nausea (7/20), decreased appetite (6/20), dysgeusia (6/20), and vomiting (4/20). Of these, only dysgeusia appeared to be dose related. No Grade 4/5 treatment related AEs or bone fragility events were reported at any of these dose levels of RXC004.

A detailed description of the RXC004 risks is provided in Section 1.7.1. Details of the pharmacology, efficacy, and safety of RXC004 is also provided in the RXC004 Investigator's Brochure.

### 5.4.4 RXC004 Intermittent Schedules

Module 3 will enroll 6 evaluable patients per Arm, with follow up for PK, pharmacodynamics and AEs.

An evaluable patient in Module 3 is defined as a patient that has received study treatment and either:

- Has completed minimum safety evaluation requirements and has received 100% of the specified RXC004 dose in Cycle 0 and at least 80% of the intended dose of RXC004 during Cycles 1 and 2.

- Has permanently discontinued study treatment due to a related adverse event

Subjects will start with a single dose of RXC004 followed by a washout of 3-7 days (Cycle 0). RXC004 schedules will commence on Cycle 1, Day 1. Each treatment cycle will be 21 days. Study treatment will continue until disease progression, intolerable toxicity or withdrawal of consent. Module 3 will start with two treatment Arms of intermittent RXC004 schedules;

- Arm 1 – 2mg QD RXC004 for 4 days, followed by 3 days off, repeated weekly for 21 day treatment cycles
- Arm 2 – 2mg QD RXC004 for 2 weeks, followed by 1 week off (21 day treatment cycles)

Patient enrolment into Arms 1 and 2 will run concurrently.

Further RXC004 monotherapy arms may be opened after review of safety and tolerability information from Arms 1 and 2, relevant data from Modules 1 and 2 and any emerging preclinical data.

[figure not shown]
Mandatory skin punch biopsies will be taken from all patients in Module 3 at baseline and while receiving treatment for analysis of pharmacodynamic markers of Wnt pathway inhibition, alongside PK sampling (see Schedule of Assessments in Appendix 9).

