**Table 7      Module 3 Dose-Interruption and Stopping Criteria**

Event	Action
Colitis events (e.g. Colitis, ileitis, enterocolitis etc.)	
Grade 1	Reduce RXC004 to a lower dose and manage per Appendix 5
Grade 2	Interrupt RXC004. Manage per Appendix 5. When event has resolved to Grade $\leq 1^a$ and steroids tapered to $\leq 10$ mg of prednisone per day (or equivalent), resume RXC004 at a lower dose.  If event recurs after re-starting study treatment, then RXC004 should be permanently discontinued.

Event	Action
Grade 3	
Interrupt RXC004. Manage per Appendix 5. When event has resolved to Grade <math>\leq 1^a</math> and steroids tapered to <math>\leq 10</math> mg of prednisone per day (or equivalent), resume RXC004 at a lower dose.
 
If event recurs after re-starting study treatment, then RXC004 should be permanently discontinued.

Grade 4	
Permanently discontinue RXC004. Manage per Appendix 5

Dysgeusia events	
Grade 1/2	
RXC004 related;
 
Consider dose reduction, depending in clinical symptoms
 
Manage per Appendix 6
 
Interrupt RXC004 treatment if dysgeusia is associated with <math>>5</math>kg weight loss from baseline

Grade 2 associated with a 10-20% decrease in body weight	
RXC004 related;
 
Manage per Appendix 6
 
Reduce RXC004 to a lower dose.

Grade 2 associated with a $>20\%$ decrease in body weight	
RXC004 related;
 
Manage per Appendix 6
 
Permanently discontinue RXC004.

Bone events	
Confirmed RXC004-related fragility bone fracture (excluding Grade 1 vertebral deformities)	
Permanently discontinue study treatment

Patients with a DEXA scan showing $\geq 7\%$ worsening in BMD at lumbar spine or total hip compared to baseline	
Permanently discontinue study treatment

Event	Action
An individual increase in $\beta$ -CTX of $\geq 350$ pg/mL from the baseline (screening) value or in individual measurement of $\geq 1000$ pg/mL	Permanently discontinue study treatment unless the patient has received clinical benefit (Investigator assessment) and continued treatment is warranted.
Other adverse events	
Grade 3-4 toxicity (1 st event)	RXC004 related: Interrupt RXC004 (max. 14 days b ), resume at the next lowest dose level when resolved ( $\leq$ Grade 2 or returns to baseline).
Grade 3-4 toxicity (subsequent recurrence of a previously experienced event)	RXC004 related; Permanently discontinue study treatment

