## 9 STATISTICS

### 9.1 Determination of Sample Size

The sample size for Module 1 is not based on a formal sample size calculation, as no formal statistical hypothesis is being tested. The estimated maximum number of patients (n=30) has been based on the expected number of cohorts and the desire to obtain adequate tolerability, safety, pharmacokinetic and pharmacodynamic data while exposing as few patients as possible to the IMP and procedures. The total number of patients required will depend upon the toxicities encountered and the number of dose cohorts required.

For Module 2, there will approximately 18 patients.

Module 3 will recruit 6 patients who are evaluable for DLT assessment per cohort.

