#### **5. Evaluable for Safety Population (Module 3)**

For Module 3, the evaluable population is defined as a patient that has received study treatment and either:

- Has completed minimum safety evaluation requirements and has received 100% of the specified RXC004 dose in Cycle 0 and at least 80% of the intended dose of RXC004 during Cycle 1 and 2.
- Has permanently discontinued study treatment due to a RXC004-related adverse event

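### Module 3's evaluability rule keeps out of the six per arm any patient who falls below 80% dosing because of related toxicity but stays on treatment

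*Protocol*

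**What the plan says.** Protocol 5.4.4 sets the size of each arm: "Module 3 will enroll 6 evaluable patients per Arm, with follow up for PK, pharmacodynamics and AEs". There are two routes to being evaluable. The first is completed minimum safety evaluations, the full Cycle 0 dose and "at least 80% of the intended dose of RXC004 during Cycles 1 and 2". The second is "Has permanently discontinued study treatment due to a related adverse event". SAP VI.J.5 carries the same two routes under the name Evaluable for Safety Population, with "at least 80% of the intended dose of RXC004 during Cycle 1 and 2" or "Has permanently discontinued study treatment due to a RXC004-related adverse event".

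Table 7 (Protocol 5.4.7) manages much related toxicity short of a permanent stop. For a first related Grade 3-4 event it says "Interrupt RXC004 (max. 14 days", followed by resumption one dose level lower. It also allows interruption for any clinically significant event at the investigator's discretion.

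Protocol 9.1 describes the same sample differently: "Module 3 will recruit 6 patients who are evaluable for DLT assessment per cohort". DLTs are defined only in Protocol 5.2.6 and 5.3.6, for Modules 1 and 2, and the SAP limits its DLT summaries to those modules. SAP IV.C asks for six evaluable patients per arm and does not mention DLTs.

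**The concern.** Module 3 asks whether intermittent schedules are tolerated. A patient who is held or reduced for related toxicity, falls below 80% and carries on treatment satisfies neither route, so recruitment continues until someone else fills the place. Membership of the six then depends partly on having tolerated the drug.

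Modules 1 and 2 work differently. Under Protocol 3.1.3 the dose threshold is 66%, and any patient with a DLT in Cycle 0 or 1 is evaluable whether or not treatment stops. A Grade 3 event that qualifies as a DLT and is managed by hold and resumption keeps the patient in the count there; in Module 3 the same course can take the patient out.

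At stake is any statement of the form x of six made by the Safety Review Committee or in the report. The SAP gives the set a name that suggests safety use but plans no table for it beyond a count of each population (SAP VII.C).

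**Working it through.** No formula, error rate or power lies behind the six, so there is no stated figure to reproduce. Two checks were made.

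**1. Which dosing patterns fall below 80%?**

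Inputs, from 5.4.4: Arm 1 is "2mg QD RXC004 for 4 days, followed by 3 days off, repeated weekly for 21 day treatment cycles", so 12 doses per cycle and 24 (48 mg) over Cycles 1 and 2. Arm 2 is 14 doses per cycle, so 28 (56 mg). Days run from Cycle 1 Day 1 to day 42; holds start on a dosing day; visit windows are ignored.

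| | Arm 1 | Arm 2 |
|---|---|---|
| 80% of planned doses | 0.8 × 24 = 19.2 | 0.8 × 28 = 22.4 |
| Doses needed | 20 (83.3%) | 23 (82.1%) |
| First failure | 5 missed: 19/24 = 79.2% | 6 missed: 22/28 = 78.6% |
| 7-day hold within days 1-42 | 20/24 = 83.3%, evaluable | 75-96%; 18 of 28 start days fail |
| 14-day hold within days 1-42 | 16/24 = 66.7%, always fails | 14/28 to 21/28 = 50-75%, always fails |

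Holds of up to 7 days (Arm 1) or 5 days (Arm 2) never fail.

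A 14-day hold running past day 42 can pass if it starts late enough:
- Arm 2: a start on day 31 loses days 31-35, giving 23/28 = 82.1%, evaluable. A start on day 30 loses six doses and fails.
- Arm 1: a start on day 36 loses four doses, giving 20/24 = 83.3%, evaluable. A start on day 32 loses five and fails.

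Reductions depend on what intended dose means, which is not defined for evaluability. Module 3 lists no lower dose levels, so 1.5 mg is an assumption taken from the indicative Module 1 levels (Protocol Table 3).
- Measured against 2 mg, a drop to 1.5 mg at Cycle 2 Day 1 in Arm 2 gives (14 × 2 + 14 × 1.5)/56 = 87.5%, evaluable. The patient stays evaluable if at least 6 full doses came first in Arm 2 (45/56 = 80.4%) or 5 in Arm 1 (38.5/48 = 80.2%).
- Measured against the reduced dose, which is the SAP IX.A convention for relative dose intensity, reduction alone never disqualifies.
- A 14-day hold followed by 1.5 mg gives 50-66.7% (Arm 1) or 37.5-75% (Arm 2) of the original dose, always below 80%.

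**2. How far could the six differ from all dosed patients?**

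Let q be the share permanently stopped for a related event and h the share below 80% for a related event but continuing. The documents give neither, so both are assumptions, and patients unevaluable for other reasons are ignored. The affected rate is q + h among all dosed and q/(1 − h) among the evaluable. Expected patients dosed to fill six is 6/(1 − h).

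| q | h | All dosed | Evaluable six | Dosed to fill six |
|---|---|---|---|---|
| 20% | 10% | 30% | 0.20/0.90 = 22.2% | 6.7 |
| 10% | 20% | 30% | 0.10/0.80 = 12.5% | 7.5 |
| 5% | 40% | 45% | 0.05/0.60 = 8.3% | 10.0 |

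The first and last rows are the smallest and largest gaps over q = 5-20% and h = 10-40%. In the middle row, the chance of at most one affected patient in six, (1 − p)^6 + 6p(1 − p)^5, is 0.83 at p = 0.125 and 0.42 at p = 0.30. This is only a yardstick; Module 3 has no such decision rule.

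**The case against.** The strongest reply is that nothing planned rests on the six. Protocol 9.2.2 and SAP IX use the Safety Population, which is everyone dosed. SAP IX.A and IX.B tabulate dose modifications with reasons, dose reductions, and events leading to interruption, reduction or withdrawal. A held patient therefore appears in both numerator and denominator. Module 3 has no escalation and no DLT rule, and further arms depend on safety information from Arms 1 and 2 without restriction to evaluable patients. All of this stands. A reader might infer that Module 3's reported safety will look better than it is; the documents do not support that.

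It is also fair that the rule catches fewer patients than a quick reading suggests. Short holds, late holds and most one-level reductions pass, and the most severe outcome, permanent discontinuation for a related event, is kept. In addition, the SAP's Module 3 schedule table lists only the two-weeks-on, one-week-off schedule, so the Arm 2 figures matter most.

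A further objection is that 80% serves PK and pharmacodynamics: the full on-treatment profile is on Cycle 1 Day 11, and Appendix 9 allocates skin biopsies by patient order within the arm. This carries little weight. A patient permanently stopped early for toxicity already counts towards the six however little was sampled, and Protocol 9.2 has separate PK and PD evaluable populations.

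**Conclusion.** The gap is real but limited. The rule excludes from the six any patient who falls below 80% for related toxicity and continues. A 14-day hold wholly inside Cycles 1 and 2 always does so, leaving 66.7% in Arm 1 and 50-75% in Arm 2. It would be wrong to conclude that every held or reduced patient drops out, or that the planned safety tables are biased. The favourable selection reaches three things: the SAP's evaluable set, the point at which an arm counts as complete, and any tolerability statement quoted on the six. Its size depends on rates the documents do not give; under the assumed ranges the six understate the affected share by about 8 to 37 percentage points (30 − 22.2 and 45 − 8.3).

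Separately, Protocol 9.1 is wrong as written: it sizes Module 3 on a DLT evaluability that exists only for Modules 1 and 2. The rest is a cheap improvement.

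**What to change.** 1. In Protocol 5.4.4 and SAP VI.J.5, add a third route: a patient below 80% because of an RXC004-related adverse event, through interruption or reduction, is evaluable for tolerability and is not replaced on that account. Leave adequacy for PK and pharmacodynamics to the separate evaluable populations in Protocol 9.2. SAP VI.J lists only the PK set, so refer to the protocol for the other.
2. Define intended dose, for evaluability, as the originally assigned dose.
3. State that Module 3 tolerability conclusions use all dosed patients, and report the number of non-evaluable patients with the reason for each.
4. In Protocol 9.1, replace the reference to DLT assessment with the 5.4.4 definition.

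The cost is a few sentences in each document. No dosing or toxicity-management rule changes, and slightly fewer patients may be needed to fill an arm. The one downside is that a counted patient may contribute less on-dose PK or biopsy data.
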